Gemtuzumab ozogamicin (GO) [Mylotarg®] is an antibody-drug conjugate used for the treatment of AML patients with myeloid cells that express the CD33 receptor.¹⁰ The FDA approved GO for the treatment of newly diagnosed CD-33-positive AML in September 2017.¹ for use alone or in combination with chemotherapy, depending on the characteristics of the patient. In April 2018, GO received marketing authorisation from the EMA for the European Union, to be used in combination with daunorubicin and cytarabine chemotherapy.^{11,12} The ALFA-0701 multicentre Phase 3 trial results demonstrated the effectiveness of GO, which ultimately led to its approval. Patients aged 50-70 years old with newly-diagnosed de novo AML were treated with GO in combination with daunorubicin and cytarabine chemotherapy. The trial demonstrated an estimated median event-free survival (EFS) of 17.3 and 9.5 months for patients receiving GO and chemotherapy or chemotherapy alone respectively and 27.5 and 21.8 months for overall survival (OS).¹

Over the years GO has been studied in multiple different combination regimens and different dosing schemes.¹² There is limited knowledge of its real-world use and outcomes as first line treatment with the recent licensed dosing (ie, 3 doses during the induction cycle). Using results from a feasibility study conducted by Adelphi Real World (ARW) and contacts with data source custodians, evidence suggests that 1L treatment with GO has been used to treat AML patients in several countries. Pfizer would like to conduct a study investigating the treatment patterns and effectiveness outcomes of 1L GO use on de novo AML patients in real-world healthcare, specifically those in the favourable and intermediate risk groups. This will allow the assessment of whether GO prescription patterns are aligned with licensed dosing/guidelines and will provide novel insights into whether the observed real-world outcomes associated with these prescription patterns are effective. The study will use a combination of AML specific data sources and a retrospective medical chart review using a Case Report Form (CRF) to conduct a multi-country study with Belgium and Austria. Such data sources were identified during a feasibility assessment and were deemed to likely capture a sufficient sample size of patients (according to the eligibility criteria outlined in [Section 9.2](#)).

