9.3.2. Outcomes

9.3.2.1. Treatment Patterns

The treatment landscape for GO will be described for all de novo AML patients treated with the drug as a 1L therapy. The following will be assessed to describe the overall treatment pathway for each patient:

Pharmacological treatment

- **Lines of therapy (LoT):** The number of LoT received by a patient from and including the index date, to the end of their observation period will be reported as a categorical (1, 2) numeric variable
- **Treatment regimen:** The number and percentage of patients receiving a given treatment regimen will be reported for each LoT, up to 2 LoT – defined as the combination of drugs (including GO)
- **Treatment setting pathway:** The treatment setting by regimen will be reported as a categorical variable using the following groups:
 - Induction, consolidation

The number of patients receiving GO in induction **AND** consolidation (in succession) will also be reported.

- **Number of doses per regimen:** The number of doses of GO in the first-line treatment regimen, broken out by first-line induction and first-line consolidation. This will be reported as a categorical (1, 2, 3, 4+) numeric variable.
- **Dosing per administration:** Actual total dose (mg) administered for GO will be reported for the first-line treatment regimen, broken out by first-line induction and first-line consolidation. This will be reported as a categorical (1, 2, 3, 4+) numeric variable.
- **Time between dosing:** Time in days between the combined chemotherapy and GO initiation (and vice versa) and time in days between each GO dose will be reported as continuous numerical variables. *Subject to availability – as multiple doses of GO are captured as one regimen; this information may not be explicitly available.*
- **Cytogenetic complete response:** Recorded for each LoT as a categorical variable:
 - Yes, No, Not examined, Undisclosed

Stem cell transplants

- **Stem cell transplants:** The occurrence of a haematopoietic stem cell transplant (HPSCT) [allogeneic or autologous] will be reported as a binary categorical variable – ‘Y’ or ‘N.’ The type of transplant will not be reported.

The feasibility of capturing/defining these data points will be assessed upon communication with data custodians and sites. Details of variable definitions will be captured in the SAP.

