9.7. Data Analysis

Detailed methodology for summary and statistical analyses of data collected in this study will be documented in a SAP, which will be dated, filed and maintained by the sponsor. The SAP may modify the plans outlined in the protocol; any major modifications of primary endpoint definitions or their analyses would be reflected in a protocol amendment.

All analyses will be conducted using Stata 17 software, version 17 or the latest available version (StataCorp, College Station, Texas).

The study is not intended to test hypotheses and is primarily descriptive in nature. Frequencies and percentages will be reported for categorical variables, including the percentage of missing/unknown data, while counts, number of missing, means, medians, SDs, SEs, first and third quartiles, minimum and maximum values will be reported for continuous numeric variables. Where applicable, all estimates will be described with accompanying 95% CIs. Time to event analyses will be conducted, with KM curves and 95% CI estimated for KM curves outputted. Finally, Sankey diagrams will be generated to aid in interpretation of the analysis of treatment patterns.

Where missing values are found in a particular variable, these will be reported either as an unknown categorical group or as the number of patients with a missing data point for continuous variables. In cases where there are large amounts of missing data or where the volume of missing data is differential between important clinical/prognostic groups, imputation may be used and reported in a sensitivity analysis with appropriate methods of imputation decided at analysis phase with the lead study analyst. The threshold of missing data which will require imputation and sensitivity analyses will be determined following initial review of the data.

Data analysis will be aligned with data extracted/collected from all data sets. Where specific variables or outcomes cannot be assessed/described subgroup analyses could be conducted for a subset of patients from certain data sources. Details of potential bias in this dataset are detailed in [Section 9.9](#).

In the event of a data source being unable to provide data for ARW led analysis, variables and outcomes will be assessed using aggregated outputs.

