9.9. Limitations of the Research Methods

Study design limitations:

- The overall sample size of patients (~230) may limit comparisons if subgroup numbers are low, such as ELN risk status (intermediate and favourable) and cytogenetic risk subgroups. However, the sample size is not substantially low in relation to the global population of interest. Furthermore, this is purely a descriptive study with no statistical comparisons and so the assessment of treatment patterns and effectiveness outcomes will not be affected by the small sample sizes.
- As this a multi-county multisource study, it is likely that there will differences in data variable availability. To mitigate this, the eCRF used for Austrian, Belgian, and German sites will be designed using knowledge of datasets known to collect data from medical records. When requesting data from the Austrian Myeloid Registry, variables will be requested in this same format where possible. Furthermore, during analysis where specific variables or outcomes cannot be assessed/described in one data source, subgroup analyses could be conducted for a subset of patients from certain data sources.
- GO-based treatment regimens and dosing schedules may differ through the different countries, adding to the complexity of the assessment of effectiveness outcomes. Subgroup analyses could be conducted for subsets of patients receiving the same or similar treatment regimens and or dosage schedules. Furthermore, dosing information per regimen may not be available in the data sources. For example, a total dose of GO may be provided, without numbers and/or timings. Nevertheless, number of doses is likely to be imputable due to prescribing guidelines and consistent quantities of GO supplied in vials (each dose). Timings of doses could be derived algorithmically, details of which would be provided in the SAP.
- The multiple cytogenetic risk groups included in the study cohorts, could similarly add complexity to the assessment of effectiveness outcomes. As a result, the analyses could include a stratification of risk group, subject to sample sizes.

- The minimum follow-up period has been set to 3 months. Consequently, for a large number of patients, OS and EFS maybe not assessable. These patients will be censored for such analyses.

Data source related limitations:

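### The GO dose in mg is assigned the reporting classes 1, 2, 3, 4+ of the dose count, under a heading that does not match its content, so the GO dosage element of the co-primary objective would not be described as written

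*Protocol*

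**What the plan says.** Protocol Section 8 lists GO dosage as one element of the second co-primary objective, separately from the number of GO doses and their timing.

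Section 9.3.2.1 gives the matching variables. The item on number of doses per regimen is "The number of doses of GO in the first-line treatment regimen, broken out by first-line induction and first-line consolidation", and it closes: "This will be reported as a categorical (1, 2, 3, 4+) numeric variable". The next item is headed *Dosing per administration*. Its definition is "Actual total dose (mg) administered for GO will be reported for the first-line treatment regimen, broken out by first-line induction and first-line consolidation", and it closes with the identical sentence and the identical classes. The item after that, on time between doses, is labelled continuous. The section ends with a general deferral: "Details of variable definitions will be captured in the SAP".

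Section 9.7 says that "means, medians, SDs, SEs, first and third quartiles, minimum and maximum values will be reported for continuous numeric variables". Section 9.9 warns that in some sources "a total dose of GO may be provided, without numbers and/or timings".

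**The concern.** Two things in the dose item do not fit together.

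- **Heading and content.** The heading points to the amount given at each administration. The definition is a total over the regimen, split by induction and consolidation. These are different quantities, and an analyst cannot tell which one the table should hold.
- **Scale and variable.** The classes 1, 2, 3, 4+ are natural for a count of doses. For milligrams they cover only the very bottom of the scale with three single values, say nothing about values between whole numbers, and pool everything from 4 upwards.

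This is the only item in Section 9.3.2.1 that reports an amount of GO. If it is tabulated as written, one listed element of a co-primary objective has no usable output. It matters most for sources that supply only a total, because there the mg amount is the main dose information and Section 9.9 expects the number of doses to be inferred from it.

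**Working it through.** The study is descriptive ("The study is not intended to test hypotheses and is primarily descriptive in nature"), so there is no sample-size, power or alpha figure to reproduce. The check sets the texts side by side and asks what each possible reading would put in the table.

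**Inputs**

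| Input | Value | Place in the protocol |
|---|---|---|
| Dose variable | total GO in mg, by induction and consolidation | Section 9.3.2.1 |
| Its heading | dosing per administration | Section 9.3.2.1 |
| Its classes | 1, 2, 3, 4+ | Section 9.3.2.1 |
| Classes of the dose count | 1, 2, 3, 4+, same sentence | Section 9.3.2.1, preceding item |
| Expected patients | 50 + 30 + 50 + 42 + 18 + 40 = 230 | Section 9.5, Table 1 |
| Any GO amount in mg | none stated | – |

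**Reading 1: the classes are milligrams.** Every total of 4 mg or more falls in the top class. Let f be the share of patients whose total is at least 4 mg. The protocol does not give f, so it is an assumption. Then

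- patients in the class 4+ = 230 × f
- patients spread over the other three classes = 230 × (1 − f)

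| f (assumed) | In 4+ | In 1, 2 or 3 |
|---|---|---|
| 0.90 | 230 × 0.90 = 207 | 230 × 0.10 = 23 |
| 1.00 | 230 × 1.00 = 230 | 0 |

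The table distinguishes only the share 1 − f, and within the class 4+ it shows no differences at all. For consolidation the denominator is the number of patients who received GO there, which the protocol does not state; the same proportions apply.

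**Reading 2: the classes are numbers of doses.** The item then has the same content, the same split by phase and the same classes as the item above it. It adds nothing in mg.

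**Reading 3: the classes number the successive administrations, with mg given for each.** The heading hints at this. The definition speaks of a total, however, and the closing sentence makes 1, 2, 3, 4+ the values of the reported variable, not an index under which mg values are listed. This reading needs two parts of the item to be set aside.

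**Does another section rescue it?** Section 9.7 has suitable summaries, but it ties them to continuous numeric variables, and Section 9.3.2.1 labels this one categorical. The neighbouring item on time between doses is labelled continuous, so the section does distinguish the two types. No other place in the protocol sets mg classes or a continuous summary for the GO dose.

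**The case against.** The strongest points on the other side are these.

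1. **The mg value is still to be collected.** Only the closing format sentence is faulty, definitions are deferred to the SAP, and Section 9.7 lets the SAP modify the plan. This stands as far as the data go: nothing is lost, and the table can be repaired. It does not remove the point. The protocol does not leave the scale open; it states one that does not fit. Section 9.7 also says that major changes to primary endpoint definitions or their analyses would go into a protocol amendment, so a silent correction in the SAP is a poor route for a co-primary element.

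2. **Alignment with licensed dosing can still be assessed in part.** The rationale says of the study: "This will allow the assessment of whether GO prescription patterns are aligned with licensed dosing/guidelines". A reader might infer that this purpose fails. The protocol does not support that. Section 7 describes the licensed dosing as three doses in the induction cycle, which is a count, and the separate items on number and timing of doses address it. What is not shown is the amount given.

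3. **The third reading would show the dose.** It is possible but conflicts with the wording, as set out above. It does mean that a sentence carried over from the item above is an inference, though a strong one given identical wording in adjacent items.

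4. **GO dosage appears only in the Section 8 list.** The cover page and the abstract name only number and timing of doses. That is correct and tempers the weight, but Section 8 is the governing list of objectives.

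5. **Dose by body surface area.** A reader might want this as well. The protocol nowhere expresses the GO dose per m², and Section 9.3.3.1 allows BMI to be supplied directly, from which body surface area cannot be recovered. Its absence is not an error in the plan.

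**Conclusion.** The point holds in a limited form. In Section 9.3.2.1 the heading, the definition and the reporting classes of the GO dose item do not agree, and the stated classes do not fit a quantity in mg. Followed as written, the output would either pool all totals of 4 mg or more or repeat the dose count. GO dosage, as listed in Section 8, would then not be described, while number and timing of doses would be.

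The size depends on doses the protocol does not state: 207 of 230 patients in one class if 90% reach 4 mg, and all 230 if 100% do. It would be tempting to say flatly that every patient falls in the top class, but that holds only under the second assumption. It would also go too far to say that the study cannot show any dose, because the fault is in the reporting format and not in data capture.

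The item should be corrected because it serves a co-primary objective and the repair is cheap. No view is taken on which dose is right.

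**What to change.** Amend the dose item in Section 9.3.2.1 so that its parts agree:

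- State whether the variable is mg per administration, total mg per phase (induction, consolidation), or both, and make the heading match.
- Label it continuous and report it with the Section 9.7 summaries, in particular median, quartiles and range, with the number missing.
- Keep 1, 2, 3, 4+ for the number of doses only.
- If both quantities are chosen, say that mg per administration is reported only for sources that record single administrations, since Section 9.9 expects some to give a total alone.

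The cost is a few lines of protocol wording, carried into the SAP. No new data item is needed for the total, because the mg dose is already planned for collection.

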Clinical outcomes will be defined using data collected if available. Clinical outcomes to be assessed include treatment response, survival outcomes, time-to event(s), minimal residual disease (MRD) status and post-transplant events.

Data sources: Data will be collected/extracted from a combination of sites and a registry. The sources include: 1 site and 1 registry in Austria (Austrian Myeloid Registry); 3 sites in Belgium; 1 site in Germany.

Study size: This study is purely descriptive and there will be no limit on the sample size in terms of patients meeting the eligibility criteria. Based on initial feasibility assessments, approximately 230 patients are expected to be eligible for inclusion, however this number will vary once sites are finalised.

Data analysis: Frequencies and percentages will be reported for categorical variables, including the percentage of missing/unknown data, while counts, number of missing, means, medians, standard deviations (SDs), standard errors (SEs), first and third quartiles, minimum and maximum values will be reported for continuous numeric variables. Where applicable, all estimates will be described with accompanying 95% confidence intervals (CI). Time to event analyses will be conducted, with Kaplan-Meier (KM) curves and 95% CI estimated for KM curves outputted. Finally, Sankey diagrams will be generated to aid in interpretation of the analysis of treatment patterns.

Data analysis will be aligned with data extracted/collected from all data sets. Where specific variables or outcomes cannot be assessed/described subgroup analyses could be conducted for a subset of patients from certain data sources.

Milestones:

- Feasibility assessment: 31 July 2022
- Start of data collection (planned): 01 November 2023
- End of data collection (planned): 30 April 2024
- Registration in the EU PAS register: EUPAS49268
- Final study report (planned): 06 September 2024

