9.3.2.2. Effectiveness Outcomes

- **Patient response to treatment regimen:** Response to each treatment regimen will be recorded as a categorical variable:
 - CR; CR with incomplete platelet recovery (CRp); CR with incomplete haematologic recovery (CRi); Partial Remission; Stable Disease; Progressive Disease; Uncertain Response; Other (before evaluation); Not evaluated/unknown

The response to stem cell transplant for relevant patients will be reported separately, again as a categorical variable:

- CR; CRp; CRi; Partial Remission; Stable Disease; Progressive Disease; Uncertain Response; Not evaluated/unknown

The event of veno-occlusive disease (VOD) following stem cell transplant for relevant patients will be recorded as a binary ‘Y’ or ‘N’ variable, where available.

The event of graft versus host disease (GvHD) following stem cell transplant for relevant patients will be recorded as a binary ‘Y’ or ‘N’ variable, where available.

- **Time to subsequent treatment:** Time in days between start of 1L induction treatment and the initiation of the next line of treatment will be reported as a continuous numerical variable.
- **MRD status:** Minimal residual disease status will be reported for each treatment regimen as a categorical variable:
 - Positive, negative, unknown
- **EFS:** Defined as the date of the start of induction treatment for de novo AML to relapse, death from any cause, or failure to achieve any of the following: CR; CRp; CRi
- **RFS:** Defined as the date of the start of first line treatment for de novo AML, to relapse, will be reported as a separate outcome specifically.

- **OS:** Defined as the date of the start of first line treatment for de novo AML, to death from any cause.

Detailed methodology for identifying the effectiveness outcomes of interest will be built in collaboration with the Pfizer team and aligned as closely with ELN 2017 guidelines⁷ were possible, whilst recognising the limitations associated with identifying complex outcomes using routinely collected real-world data. As such, sensitivity analyses will be applied where necessary, with full details to be documented in the SAP.

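### Transplant type is barred from the report while GvHD is listed among undefined relevant patients, so the GvHD percentage may understate the risk among allogeneic recipients by an amount a reader cannot see

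*Protocol*

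**What the plan says.** Protocol section 9.3.2.1, under stem cell transplants, defines one yes/no variable for the occurrence of a haematopoietic transplant, with both graft types named in brackets as qualifying. The entry ends: "The type of transplant will not be reported".

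Section 9.3.2.2 then lists three items that follow a transplant:

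- Response: "The response to stem cell transplant for relevant patients will be reported separately".
- VOD: "The event of veno-occlusive disease (VOD) following stem cell transplant for relevant patients" is a yes/no variable, where available.
- GvHD: "The event of graft versus host disease (GvHD) following stem cell transplant for relevant patients will be recorded as a binary" yes/no variable, again where available.

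All three refer to relevant patients. The protocol does not define the term and nowhere restricts it to allogeneic recipients.

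The Abstract (section 4) includes these items among the clinical outcomes to be assessed, ending its list with "minimal residual disease (MRD) status and post-transplant events". Section 9.7 sets the summary: "Frequencies and percentages will be reported for categorical variables, including the percentage of missing/unknown data". Section 9.3.2.1 leaves the details of variable definitions to the SAP.

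**The concern.** GvHD is understood here as a complication of donor grafts, so the group at risk is the allogeneic recipients. The protocol lists GvHD as an outcome and will summarise it as a percentage, but bars from the report the one variable that identifies that group. This is a stated rule, not a detail left open for the SAP. An SAP that followed it could not show the allogeneic denominator.

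Two things are at stake. First, the GvHD percentage could be diluted by patients who are not at risk, to a degree the reader cannot judge. Second, section 9.3.2.1 presents these variables as describing each patient's treatment pathway, and section 7 names allogeneic transplantation as a consolidation route that depends on eligibility. A pooled yes/no variable cannot show how many patients took that route.

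**Working it through.** **Figures in the protocol.** There is no figure for the number transplanted, the autologous share or the GvHD risk. The only related figure is the expected study size of about 230, which Table 1 reproduces: 50 + 30 + 50 + 42 + 18 + 40 = 230. It does not enter the calculation below.

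**Step 1: what the denominator is.** There are two readings of relevant patients.

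- *All transplanted patients.* This is the natural reading. The same phrase governs response and VOD, and the text ties neither of those to one graft type. Autologous recipients are then in the GvHD denominator.
- *Allogeneic recipients only.* Section 9.7 calls for a frequency and a percentage. The frequency divided by the percentage gives the denominator, which would be the number of allogeneic recipients assessed. Transplant type would in effect be reported, against section 9.3.2.1.

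The text needs a correction under either reading.

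**Step 2: size under the natural reading.** Let g be the GvHD risk among allogeneic recipients and a the autologous share of transplants. Assume no GvHD risk after autologous transplant. Then:

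pooled GvHD percentage = g × (1 − a)

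relative loss = [g − g × (1 − a)] / g = a

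The relative loss does not depend on g. The values of g and a below are assumptions, not protocol figures.

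| Autologous share a | Pooled % if g = 50% | Pooled % if g = 30% | Relative loss |
|---|---|---|---|
| 0% | 50 × 1.00 = 50.0 | 30 × 1.00 = 30.0 | nil |
| 5% | 50 × 0.95 = 47.5 | 30 × 0.95 = 28.5 | 5% |
| 10% | 50 × 0.90 = 45.0 | 30 × 0.90 = 27.0 | 10% |
| 20% | 50 × 0.80 = 40.0 | 30 × 0.80 = 24.0 | 20% |
| 30% | 50 × 0.70 = 35.0 | 30 × 0.70 = 21.0 | 30% |

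**Step 3: whether a reader can correct it.** Recovering g needs the pooled percentage divided by (1 − a). The share a can only be known if type is reported, and section 9.3.2.1 rules that out.

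**The case against.** The strongest case against has four parts.

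1. *The mixed denominator is inferred.* No sentence says that the GvHD percentage is taken over both graft types. Relevant patients could mean a different set for each outcome, and variable definitions are deferred to a SAP that is not at hand. This stands as a limit: the mix is the natural reading, not an express statement. It does not remove the point, because the bar on reporting type is in the protocol itself and conflicts with the alternative reading too.
2. *Not reported is not the same as not collected.* This is correct. A reader might infer that sites will not record type. The protocol does not say so, and an allogeneic denominator may be obtainable from the data.
3. *The percentage would still mean something.* This is also correct. A reader might infer that a pooled figure cannot be interpreted. It remains a valid proportion of transplanted patients and, with no autologous risk, a lower bound for the allogeneic risk.
4. *The dilution may be negligible.* Section 7 names only allogeneic transplantation as transplant consolidation, which may mean that autologous procedures are few. At a share near 0% nothing is lost. This stands, and the protocol cannot settle it.

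It is also true that GvHD, VOD and transplant response appear in none of the objectives in section 8, and that section 9.7 describes a study that tests no hypotheses.

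**Conclusion.** The point holds as a minor reporting defect. The protocol forbids reporting the variable that defines who is at risk of GvHD while listing GvHD as an outcome among patients it does not define. On the natural reading, the published percentage understates the allogeneic risk by the factor (1 − a), and a reader can neither see nor undo this.

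The size depends on an autologous share that the protocol does not give: nil at 0%, 5% relative at 5%, 30% relative at 30%. This rests on two assumptions, that relevant patients means all transplanted patients and that autologous recipients carry no GvHD risk. The documents do not support the stronger conclusions that the percentage is certainly a mixture or that it is uninterpretable. No objective, sample size, survival estimate or error rate is affected.

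**What to change.** In section 9.3.2.1, delete the sentence "The type of transplant will not be reported" and report transplant as none, allogeneic, autologous or unknown, where the source captures type. In section 9.3.2.2, replace relevant patients in the GvHD entry with allogeneic recipients as the denominator. Showing VOD and transplant response by type is optional, since nothing in the protocol contradicts a pooled description of those.

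The cost is one extra field if type is not already captured, plus some unknown entries. The latter are most likely from the Austrian Myeloid Registry, because section 9.3 says its variables are not all explicitly known.

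The change is best made before charts are abstracted. Section 9.6 provides for fully anonymised German data with no way back to the patient, and Table 1 expects 40 of the 230 patients (40 / 230 = 17%) from that site. A field omitted at entry may not be recoverable there. The change concerns reporting only and has no bearing on patient management.
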